Continuous Negative Abdominal Pressure in Acute Respiratory Distress Syndrome
(CNAP in ARDS)

January 05, 2018

Investigators

[name]

[name]

[name]

[name]

[name]

[name]

[name]

BACKGROUND AND RATIONALE

Adult respiratory distress syndrome (ARDS) is a serious pulmonary disease affecting adults and children. It has a high mortality and there is no specific therapy. The mortality is high (approx. 40% in severe cases) and this has not changed in the last 20 years (Bellani, 2016). Mechanical ventilation is the mainstay of management, and this assists the patient by increasing oxygenation and removal of carbon dioxide. Despite optimizing tidal volume, driving pressure and positive end-expiratory pressure (PEEP), patients with ARDS develop large areas of atelectasis (collapse) and poor oxygenation (Slutsky, 2013). There are few additional ventilator approaches that have proven to be effective in preventing this type of injury.

A major aim of ventilator support is recruitment of atelectatic (i.e. de-aerated) lung, but while this is supported by excellent rationale and laboratory data, the recent large clinical trial has revealed that recruitment with positive pressure worsened patient outcome (Costa Leme, 2017). Most atelectasis in ARDS occurs in the dorsal (dependant, lower-most) lung regions, and these are near the diaphragm.

The main ways to recruit lung are to increase the airway distending pressure (but this overexpands and damages the already-aerated lung regions); or, to turn the patient into the prone position (but clinicians are reluctant to utilize this approach – despite evidence that it may increase survival (Bellani, 2016). Continuous Negative Abdominal Pressure (CNAP) aims to selectively recruit basal atelectatic areas of lung, while enabling the patient to remain in the supine (usual) position (Chierichetti, 2012; Yoshida, 2017).

PREVIOUS RELATED WORK

We have extensive data from rodent and large animal experiments in our laboratory that demonstrate the effectiveness of a novel approach: we applied negative pressure to the abdomen in order to selectively recruit lung that lies against the diaphragm.

We have demonstrated, in rodents (Chierichetti, 2012), and in a large animal [i.e. anesthetized pig with lung injury] model (Yoshida, 2017) that CNAP augments oxygenation and improves compliance, and importantly, it reduces the degree of subsequent lung injury. In the rodent application, the animals developed hypotension, but not in the large animal model. We have recently completed a Phase 1 study on healthy volunteers (HSC REB#1000057680). This demonstrated that the CNAP is well tolerated in awake healthy subjects and caused no adverse effects. Others have used a variation of this approach in anesthetized pigs (Valenza, 2005) and in humans with ARDS (Valenza, 2003), but they did not use recruitment maneuvers; and, the devices used did not encircle the abdomen or achieve effective transmission of negative pressure across the abdominal wall.

In these applications, the approach did not augment ventilation but, neither did they cause any adverse impact.

Finally, the technique has been used (although for a different indication) to reduce elevated intra-abdominal pressure in critically ill patients (Bloomfield, 1999 #247).

Device: A patent (US) application has been filed for the device (owned by SickKids)

RESEARCH OBJECTIVES AND HYPOTHESIS

We wish to perform a safety, 'Phase 2' study in patients that have been diagnosed with Acute Respiratory Distress Syndrome (ARDS) to determine primary safety and efficacy of using CNAP.

Safety (Stop rules)

↓mean arterial pressure <60 mmHg or ↓15%
(despite 500 mL fluid or increase norepinephrine)
↓SpO2 (drop >5%)
↓PaO2/FiO2 >20% .

Efficacy ↑PaO2/FiO2 >20%

RECRUITMENT PROCESS

Patients will be recruited from the Intensive Care Unit, following completion of informed consent from the patient or legally authorized substitute decision maker (SDM) (see Consent Form). Please see "Inclusion and Exclusion criteria"

POPULATION TO BE STUDIED

Patients with ARDS. Weight range 40-100 kg. Ventilated with positive pressure ventilation and a P/F ratio ≤200 mmHg with PEEP ≥5 cmH2O

Inclusion Criteria:

- 1) Patients ≥ 18 years old
- 2) Patients with moderate to severe ARDS as per the Berlin definition (PaO2/FiO2 ≤200mmHg) (Ranieri, 2012)
- 3) Patients with absence of any significant cardiopulmonary disease

Exclusion Criteria:

- 1) Contraindication to CNAP
 - a. open abdominal wounds or drainage tubes
 - b. Acute brain Injury with intracranial pressure >30 mm Hg or cerebral perfusion pressure <60 mmHg
 - c. Decompensated heart insufficiency or acute coronary syndrome
 - d. Major hemodynamic instability: Mean arterial pressure lower than 60 mm Hg despite adequate fluid resuscitation and two vasopressors or increase of vasopressor dose by 30% in the next 6 hours.
 - f. Unstable spine, femur, or pelvic fractures
 - g. Pregnancy
 - h. Pneumothorax
- 2) Contraindication to EIT electrode placement
Burns, chest wall bandaging limiting electrode placement
- 3) Severe liver insufficiency (Child-Pugh score > 7) or fulminant hepatic failure
- 4) Major respiratory acidosis or PaCO₂ > 60 mmHg
- 5) Severe COPD (according to the GOLD criteria defined as severe = FEV1: 30-50% or very severe = FEV1 < 30%)
- 6) Clinical judgement of the attending physician

INTERVENTIONS AND RESEARCH PROCESS

Pre-Human Testing: The device has been extensively tested (the first prototype was successfully tested on a pig with good success (Yoshida, 2017).

The current device has undergone a closed loop stress test for 24 hours (-10 cmH₂O) and showed no signs of failure. This device was made in the laboratory of [name] in the department of Biomedical Engineering.

The device has also been tested on a Mannequin (please see photograph in the appendix), with no leakage.

Protocol (summarized in Flow Chart):

- 1) Eligible patients will be identified with research coordinators by daily screening in the intensive care unit
- 2) Consent for participation will be obtained from the patient's substitute decision maker
- 3) Prior to starting the application of CNAP, patients will be sedated deeply with sedatives and/or opioids, and will be paralyzed with a continuous infusion of rocuronium, if not started (7 µg/kg/min).
- 4) Also we will install the EIT to visualize the ventilation pattern.
- 5) Baseline measurement (see Appendix, ARDS Registry Form)

- a) Lung Mechanics
- b) Pressure-Volume Curve,
- c) determination of Recruitability, and
- d) Fluid Responsiveness.

6) Stage 1

the CNAP device is attached to the abdomen (but no suction), and a complete set of vital signs recorded.

7) Stage 2

a suction is applied to the CNAP device until chamber pressure will reach -5cmH₂O, and vital signs carefully monitored. If no impact, go to stage 3.

8) Stage 3

the suction level will be increased until esophageal pressure will decrease by -3cmH₂O, as per the primary team, and vital signs recorded. If no impact, go to next stage after discuss with the clinical team and attending physician responsible for the patient's care

9) Stage 4 & 5

First, lung recruitment with CPAP 40cmH₂O for 10sec. Then the suction will be applied until esophageal pressure will decrease by -3cmH₂O, as per the primary team, and vital signs recorded.

10) Stage 6

when the study is finished, and the device removed, monitoring will continue –along with primary team- as per usual ICU care.

At each stage, if any concern (Safety-Stop rules, see above), the primary care team will immediately stop the CNAP. If effective (Efficacy, see above), CNAP will continue for 2 hours.

If the device appears to have helped, it can (at the request of the care team) be left in place for a total of 24h.

A SCHEMATIC of the study protocol is appended (Flow chart).

The following parameters will be recorded (see Flowchart & Case report form).:

Hemodynamic (S/M/DAP, HR, CVP)

Respiratory Mechanics (RR, VT, mPaw, PIP, Pplat, PEEP, end-exp. Pes, EIT)

Gas Exchange (FiO₂, SpO₂, PaO₂, PaCO₂)

Abdominal Pressure (Pbladder)

ANTICIPATED OUTCOME

We anticipate no significant impact on cardiovascular physiology; we expect some improvement of the P/F ratio, lung compliance and ventilation distribution.

SAMPLE SIZE AND JUSTIFICATION

A convenience sample size of 20 patients will be invited to participate. We anticipate that patient oxygenation will increase with CNAP application in conjunction with positive pressure ventilation vs positive pressure ventilation alone.

Because we will use sensitive markers of any impact on respiratory or circulator parameters (including patient reported dyspnea, and key parameters (see Data Sheet), this will facilitate detection of any potentially adverse effects.

RESEARCH PROCEDURES

Analysis will consist of inspection of the data associating transition to and withdrawal from CNAP.

We estimate that the total time in the CNAP device might be around 6 hours, but it could take less time or more time. Throughout this period, close monitoring will ensure comfort and safety.

SAFETY PROCEDURES

The testing will be performed beside in the Intensive Care Unit at St Michael's Hospital. A staff physician will be present, and dedicated to monitoring the subject and ensuring safety. No medications will be administered. All data will be digitized and securely stored.

DEFINITION AND MEASUREMENTS

Demographic Data: Demographic data will be obtained from the patient's medical file: Age, gender, height and weight, Admission diagnosis, Cause of acute respiratory failure, Significant comorbidities (COPD, CHF, other chronic organ insufficiency), Days on ICU and days on MV (days), APACHE II severity score and SOFA score on the day of the test, etc (See case report form).

Electric Impedance Tomography: EIT data will be recorded using the PulmoVista®500 (Dräger, Lübeck, Germany) with 16-electrode silicon belt, placed on the perimeter defining a cross sectional plane of the thorax at the level of the 5th intercostal space (parasternal line). In all patients, EIT data will be recorded at each stage, and analyzed with the dedicated analysis tool (Dräger EIT analysis Tool 6.1). EIT images will be divided into two (and four) zones, each covering 50% (and 25%) of the ventro-dorsal direction, for the analysis of ventilation pattern.

Airway Pressure, Esophageal Pressure and Flow: The esophageal balloon (Copper Surgical, Trumbull, CT, USA) will be inflated by 1.0 ml of air volume. If applicable, we will record the data as follows (if not applicable, we will record the data from the ventilator monitor and portable monitor). The proximal end of the catheter is connected to a pressure transducer and recording equipment (MP150; Biopac systems, Goleta, CA,

USA). Airway flow and pressure sensors will be connected to the respiratory circuit, proximal to the Y-piece. The flow will be measured through a pneumotachograph (Fleish No. 2; Metabo; Epalinges, Switzerland) adequately calibrated using a 1 L syringe to obtain integration of 1 L equals to 1 Volt. Proximal airway pressure will be measured using a differential pressure transducer (TSD160series: Biopac systems, Goleta, CA, USA) previously calibrated at 10 and 0 cmH₂O using a water column. Signals will be acquired with an analogue-digital converter (MP150; Biopac systems, Goleta, CA, USA), sampled at 200 Hz and stored in a laptop computer for subsequent off-line analysis (Acqknowledge 4.3, Biopac Systems).

- 1) Transpulmonary pressure (PL): Maximal values of PL = [airway pressure – esophageal pressure] will be recorded as peak PL. We also will calculate Δ PL as the difference between the airway driving pressure and Δ esophageal pressure (i.e. airway pressure – PEEP – Δ esophageal pressure) corresponding to the same time phase and we will pick up the maximal value as peak Δ PL. Plateau PL will be calculated as [airway pressure - esophageal pressure] after making an inspiratory hold (i.e. zero flow phase). Expiratory PL will be calculated as [airway pressure - esophageal pressure] after making an expiratory hold.
- 2) Airway pressure and flow: Plateau pressure, peak airway pressure and PEEP will be measured, as previously described (Henderson, 2017). Tidal volume will be calculated as integral of flow. Considering the total stretching pressure across respiratory system (lung + chest wall) with spontaneous breathing during mechanical ventilation, driving pressure will be calculated as the sum of [plateau pressure – PEEP] and the changes in esophageal pressure corresponding to plateau phase when compared with passive conditions (Yoshida, 2013). During muscle paralysis, driving pressure was calculated as [plateau pressure – PEEP]. The dynamic compliance of the respiratory system was defined as: [VT/ driving pressure].

Hemodynamics: Arterial blood pressure and heart rate will be continuously monitored on the ICU bedside monitor.

Arterial Blood Gas: pH, PaCO₂, PaO₂ will be measured by standard clinical technique using the ICU blood gas analyzer.

STATISTICAL ANALYSIS

Statistical analysis will be performed using standard software SPSS13.0 for Windows (SPSS, Chicago, IL, USA). The results are expressed as mean \pm standard deviation. 1-way analysis of variance for repeated measures will be used to evaluate the impact of time. In the post hoc analysis to separate differences between the means, a Tukey's pair-wise multiple comparison test will be used. All tests were two-tailed, and differences were considered significant when $p < 0.05$

REFERENCES

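### The written haemodynamic safety criterion leaves out MAP falls that treatment reverses, and the visible plan does not say that such falls, or the rescue given, will be reported

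*Combined protocol and SAP*

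**What the plan says.** Under RESEARCH OBJECTIVES AND HYPOTHESIS the study is "to determine primary safety and efficacy of using CNAP". Directly below, the safety entry is a set of stop rules. The haemodynamic one is MAP below 60 mmHg or a 15% fall, followed on its own line by "despite 500 mL fluid or increase norepinephrine". The SpO2 and PaO2/FiO2 rules beside it carry no such qualifier.

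Under INTERVENTIONS AND RESEARCH PROCESS:
- The recorded circulatory items are "Hemodynamic (S/M/DAP, HR, CVP". The list points to a flow chart and case report form that are not in the supplied text.
- After Stage 2 the instruction is "If no impact, go to stage 3", and after Stage 3 "If no impact, go to next stage after discuss with the clinical team and attending physician". Impact is not defined.
- At every stage the care team is to halt CNAP at once on any concern, with the stop rules cited in parentheses.

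SAMPLE SIZE AND JUSTIFICATION relies on sensitive markers ("Because we will use sensitive markers of any impact on respiratory or circulator parameters") and refers to a Data Sheet, also not in the text. RESEARCH PROCEDURES says "Analysis will consist of inspection of the data associating transition to and withdrawal from CNAP". STATISTICAL ANALYSIS says "1-way analysis of variance for repeated measures will be used to evaluate the impact of time". No section defines a count of stop events, of treated pressure falls or of rescue treatment.

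**The concern.** A rule for when to stop and a definition of what to report serve different purposes, and this plan writes only the first. Allowing a fluid bolus or more norepinephrine before abandoning the intervention is sensible at the bedside. If the same rule is also the safety result, a fall that needed treatment and responded to it meets no criterion.

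This matters because safety is a primary aim and the ANTICIPATED OUTCOME section expects no significant cardiovascular effect. The background is mostly reassuring but mixed: hypotension in rodents, none in the large animal model, and no adverse effects in healthy volunteers. A flat MAP across stages would seem to confirm the expectation whether the device was neutral or the pressure was held up by treatment.

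**Working it through.** The plan has no haemodynamic event rate or power figure to reproduce; the 20 patients are a convenience sample. The check is mainly a comparison of sections.

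**1. What the qualifier removes.** If it covers both limbs, every reversed fall to below 60 mmHg, or of 15%, lies outside the rule. If it covers only the 15% limb, a reversed fall lies outside only when a 15% drop still leaves MAP at or above 60 mmHg. That needs a baseline of at least 60 / 0.85 = 70.6 mmHg. The layout favours the first reading, but some treated falls escape under either.

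**2. Is support recorded?** For oxygenation, FiO2 is listed with PaO2 and the criterion is their ratio, so the response is read against the support given. For MAP, the visible list has no equivalent. Yet exclusion 1d uses the number of vasopressors and a 30% dose increase to define instability, so the protocol itself treats dose as informative. As written, that exclusion does not remove patients on stable vasopressors with an adequate MAP, so titration during CNAP is foreseeable.

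**3. Is rescue reported?** The two analysis statements are inspection around transition and withdrawal, and repeated-measures ANOVA on time. Neither mentions rescue. A stage mean is also a weak detector of single events. A 15% fall in one of 20 patients moves it by 0.15 × baseline / 20. For assumed baselines of 70 and 90 mmHg that is 10.5 / 20 = 0.53 and 13.5 / 20 = 0.68 mmHg.

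**4. Illustration on assumed rates.** Let p be the true proportion of patients with a fall to threshold and r the share of falls reversed by rescue, with the qualifier covering both limbs. Neither p nor r is in the documents. The proportion meeting the written rule is q = p(1 − r), the expected count is 20q, and the chance of at least one event is 1 − (1 − q)^20.

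| p | all falls counted | r = 0.5 | r = 0.8 | r = 1.0 |
|---|---|---|---|---|
| 0.10 | 2.0 (0.878) | 1.0 (0.642) | 0.4 (0.332) | 0 (0) |
| 0.20 | 4.0 (0.988) | 2.0 (0.878) | 0.8 (0.558) | 0 (0) |
| 0.30 | 6.0 (0.999) | 3.0 (0.961) | 1.2 (0.710) | 0 (0) |

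Cells are the expected number of patients and, in parentheses, the chance of at least one. If no fall is reversed, the two counts agree. The table describes what meets the written criterion. It does not show what the recorded pressures would reveal.

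**The case against.** The strongest reply is that much of the point turns on forms nobody can see here. The parameter list defers to a case report form and flow chart, the key parameters to a Data Sheet, and the baseline measurements to a registry form. A reader might infer that rescue data are not collected. The documents do not support that, so on data capture this is a request to confirm.

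A reader might also infer that a rescued fall would be invisible. That is too strong. MAP is recorded by stage and arterial pressure is monitored continuously. SAFETY PROCEDURES says data are digitised and stored, and the analysis looks at transition and withdrawal. A fall present at a stage reading would show, and one on the monitor could. What may be lost is a fall corrected before the reading, and the fact that a stable value needed treatment.

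Nor can the gap be said only to understate hypotension. The qualifier works in that direction, but an unrecorded vasopressor reduction during a stage would lower MAP and look like a device effect.

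Finally, the stop rule is ordinary and patients have other protection: a dedicated staff physician, exclusion of the most unstable patients, and the halt on any concern, which covers Stages 4 and 5 as well. All of this stands. None of it says that treated falls or rescue will be reported.

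**Conclusion.** The point holds as a minor gap in the safety definition. The written haemodynamic criterion does not count a MAP fall that is treated and reversed, certainly for the 15% limb and most naturally for both. The visible plan neither lists the support behind a stage MAP nor commits to reporting rescue. A stable stage MAP is therefore open to two explanations, and unrecorded dose changes in either direction would blur the stage comparison.

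The size cannot be estimated: it depends on how often MAP falls and how often rescue works, and the documents give neither. If no fall is treated, nothing is lost from the event count. Confidence is good on what the criterion says and low on whether dose and fluid are already captured. The point is no argument that the stop rule is unsafe. The statement under SAFETY PROCEDURES that no drugs are given conflicts with the planned sedation, rocuronium and rescue norepinephrine, but that is a separate wording matter and carries no weight here.

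**What to change.** Leave the stop rule and the halt on any concern as they are. Add a reporting definition. A haemodynamic safety event is:

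1. any MAP below 60 mmHg, or fall of 15% or more from the pre-CNAP baseline, that is sustained for a prespecified time or treated; or
2. any fluid bolus or norepinephrine increase given for a MAP fall during CNAP, whether or not the fall is reversed.

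The sustained time is a clinical choice to fix before enrolment. State whether the qualifier covers one MAP limb or both. Confirm that norepinephrine dose, up or down, and fluid volume are captured at each stage, or add them, and show both beside the stage MAP.

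The cost is one definition, one clarification and at most a few chart fields. Thresholds, stages and sample size do not change. The downside is a higher reported event rate that will include some falls not caused by CNAP.

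### The intracranial and cerebral perfusion pressure limits that bar a brain-injured patient from CNAP at entry are not carried into the stop rules or the 2 h and 24 h continuation rules

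*Combined protocol and SAP*

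**What the plan says.** All references are to the combined protocol and SAP.

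- **Entry** (Population to be Studied, exclusion 1b, under contraindications to CNAP): "Acute brain Injury with intracranial pressure >30 mm Hg or cerebral perfusion pressure <60 mmHg". No other listed criterion names brain injury, and none says what to do when ICP is not measured. Exclusion 6 lets the attending physician exclude on clinical judgement.
- **Stop rules** (Research Objectives and Hypothesis): the blood pressure rule is "mean arterial pressure <60 mmHg or ↓15"%, qualified by "despite 500 mL fluid or increase norepinephrine". The other two rules are an SpO2 drop above 5% and a PaO2/FiO2 (P/F) fall above 20%.
- **Application** (Interventions and Research Process): "At each stage, if any concern (Safety-Stop rules, see above), the primary care team will immediately stop the CNAP".
- **Continuation** (same section): "If effective (Efficacy, see above), CNAP will continue for 2 hours". Efficacy is a P/F rise above 20%. If the device seems to have helped, the care team may ask for it to "be left in place for a total of 24h".
- **Recorded variables** (same section): the list of circulatory variables begins "Hemodynamic (S/M/DAP, HR, CVP". ICP and CPP are not in the printed list, which refers on to a flow chart and case report form that were not supplied.
- **Patient state** (step 3): "patients will be sedated deeply with sedatives and/or opioids, and will be paralyzed with a continuous infusion of rocuronium".

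**The concern.** The protocol treats ICP above 30 or CPP below 60 mmHg in acute brain injury as a reason not to apply CNAP. That reasoning should hold during exposure as well as before it. The protocol already does this for blood pressure: a MAP of 60 mmHg appears both in an entry exclusion (1d) and in the stop rules. The 1b limits are also numerical, and in a monitored patient they can be read at the bedside, yet they appear only at entry.

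A patient who enters inside the limits and crosses them on CNAP can meet the efficacy criterion and no stop rule. The printed instruction is then to continue for 2 h. This is a safety study in deeply sedated, paralysed patients, in whom most clinical neurological signs are unavailable. What is at stake is when exposure ends for such a patient. The efficacy analysis is not affected.

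**Working it through.** **Inputs from the protocol.** Entry limits in 1b: ICP >30, CPP <60 mmHg. MAP stop limits: below 60 mmHg, or a 15% fall. Efficacy: P/F rise above 20%.

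**Assumptions.** The protocol does not define CPP and gives no MAP, ICP or CPP values. I take CPP = MAP − ICP, hold ICP constant unless stated, and use ICP 10, 20 and 30 mmHg. There is no figure in the plan to reproduce.

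**Step 1: CPP when the MAP limit is first reached.** Entry MAP = entry CPP + ICP. The limit first reached is the larger of 0.85 × entry MAP and 60. The 60 mmHg limb comes first only if entry MAP is below 60/0.85 = 70.6.

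For a patient entering at CPP 60:

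- ICP 10: entry MAP 70; 0.85 × 70 = 59.5, so the 60 limb comes first; CPP = 60 − 10 = 50.
- ICP 20: entry MAP 80; 0.85 × 80 = 68; CPP = 68 − 20 = 48.
- ICP 30: entry MAP 90; 0.85 × 90 = 76.5; CPP = 76.5 − 30 = 46.5.

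The same calculation for higher entry CPP gives:

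| Entry CPP | ICP 10 | ICP 20 | ICP 30 |
|---|---|---|---|
| 60 | 50.0 | 48.0 | 46.5 |
| 70 | 58.0 | 56.5 | 55.0 |
| 75 | 62.3 | 60.8 | 59.3 |
| 80 | 66.5 | 65.0 | 63.5 |

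**Step 2: where the MAP rule does protect CPP 60.** Requiring 0.85 × (CPP + ICP) − ICP ≥ 60 gives entry CPP ≥ (60 + 0.15 × ICP)/0.85, which is 72.4, 74.1 and 75.9 mmHg for ICP 10, 20 and 30. Below about 72 to 76, CPP can pass under 60 before the MAP limit is reached. Reaching that limit does not itself stop CNAP, because fluid or norepinephrine may be tried first.

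**Step 3: a case followed through the printed rules.** Entry: MAP 90, ICP 20, CPP 70, P/F 120. On CNAP: MAP 79, ICP 20, P/F 150, SpO2 unchanged.

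- MAP fall: (90 − 79)/90 = 12.2%, and MAP is above 60, so the MAP rule is not met.
- CPP: 79 − 20 = 59, inside the 1b contraindication.
- P/F: 150/120 = +25%, so the efficacy criterion is met and the printed rule is to continue for 2 h.

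**Step 4: a rise in ICP alone.** MAP stays at 90 and ICP goes from 25 to 31. CPP goes from 90 − 25 = 65 to 90 − 31 = 59. Both 1b limits are crossed. With SpO2 and P/F not falling, no printed stop rule is met.

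**The case against.** The strongest reply is that clinicians are not left without safeguards.

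- Moves from Stage 2 to 3 and from Stage 3 onward require no impact on the previous step, and the second also needs discussion with the attending physician. A MAP fall from 90 to 79 might well count as an impact. This stands as mitigation, but these gates govern escalation and not the 2 h hold.
- The stop instruction speaks of any concern, a dedicated staff physician is present (Safety Procedures), and exclusion 6 allows case-by-case exclusion. These also stand, but the words about concern point back to the stop list, and none of these safeguards adds an ICP or CPP number to it.
- Other exclusions that could arise during CNAP (PaCO₂ >60 mmHg, pneumothorax, acute coronary syndrome) are not stop rules either. That is true, so 1b is not a lone omission, but the gap remains.
- An unqualified ICP/CPP stop would let one brief reading end CNAP, while the MAP rule allows treatment first. This is a fair point, and the fix below takes it in.

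A reader might also infer more than the documents support:

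- **That CPP could reach 40 or 30 (60 − 20, 60 − 30) before the MAP rule acts.** With ICP constant it cannot. A patient passing 1b at ICP 20 or 30 enters with MAP of at least 80 or 90, so the 15% limb is met first, at CPP of at least 48 or 46.5.
- **That the protocol gives clinicians no ICP or CPP limit at all.** Exclusion 1b prints one and calls it a contraindication to CNAP. What is missing is its repetition in the stop and continuation rules.
- **That the rules require 24 h of exposure.** The 24 h extension is a permission, at the care team's request. Only the 2 h continuation is worded as a rule.
- **That ICP goes unrecorded.** The flow chart and case report form were not supplied and may include it.

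**Conclusion.** The point holds as a modest safety gap in the printed text. Brain-injured patients inside the 1b limits are eligible, and nothing in the stop or continuation rules carries those limits into the exposure period. Under constant ICP, a patient entering at CPP 60 would be 10 to 13.5 mmHg below the entry limit when the MAP limit is first reached. From an entry CPP of about 72 to 76 upward, the MAP rule does keep CPP at 60 or above, provided ICP does not rise.

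The size is uncertain and probably small. All pressures above are assumed. The documents give no evidence that CNAP raises ICP. They report hypotension in rodents but not in the large-animal model, and no adverse effects in volunteers. The number of brain-injured patients is not stated; none to a few of the 20 is an assumption.

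A reader might infer that acute brain injury, or at least brain injury with unmeasured ICP, must be excluded. The documents do not settle this. Exclusion 1b is silent on missing ICP, acute brain injury is undefined, and a blanket exclusion could remove mild cases that exclusion 6 already leaves to the attending physician. That choice belongs to the investigators. This is a change to consider.

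**What to change.** For patients with acute brain injury whose ICP is already monitored clinically, add one line to the stop rules: ICP >30 mmHg or CPP <60 mmHg, sustained despite prompt treatment. Check it at each stage and throughout any 2 h or 24 h continuation. The treatment qualifier keeps the rule in line with the MAP rule, so that a brief reading does not end CNAP. The investigators should state how long counts as sustained. If the flow chart or case report form already carries such a limit, copy it into the protocol body.

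No ICP monitor should be placed for the trial. The cost is one line of text and possibly a few extra stops.

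### If any patient is stopped early because P/F falls, the planned repeated-measures ANOVA in its usual complete-series form compares stages only in patients whose P/F did not fall

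*Combined protocol and SAP*

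**What the plan says.** The stop rules (RESEARCH OBJECTIVES AND HYPOTHESIS, Safety) act on three recorded variables: MAP ("mean arterial pressure <60 mmHg or ↓15" per cent, qualified by "despite 500 mL fluid or increase norepinephrine"), an SpO2 drop above 5%, and a P/F fall above 20%. The efficacy criterion in the same section is a P/F rise above 20%.

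The Protocol section sets Stage 1 as the no-suction reference: "the CNAP device is attached to the abdomen (but no suction), and a complete set of vital signs recorded". Suction then rises in steps. Stage 2 ends with "If no impact, go to stage 3" and Stage 3 with "If no impact, go to next stage after discuss with the clinical team and attending physician". After Stage 6 the text adds "At each stage, if any concern (Safety-Stop rules, see above), the primary care team will immediately stop the CNAP" and "If effective (Efficacy, see above), CNAP will continue for 2 hours".

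STATISTICAL ANALYSIS gives one inferential method: "1-way analysis of variance for repeated measures will be used to evaluate the impact of time", followed by Tukey comparisons. It names no outcome, time points, analysis set or missing-data rule. RESEARCH PROCEDURES adds that the data around the start and withdrawal of CNAP will be inspected. The flow chart and case report form are cited but are not in the text.

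**The concern.** A classical repeated-measures ANOVA needs a value at every time point. A patient stopped at Stage 2 or 3 has no later value under suction, so the usual form drops that patient from every comparison, including stages already measured. When the stop was for P/F, the remaining patients are there partly because their P/F did not fall. Their mean change is then pushed upward, and the test can reject when CNAP does nothing on average. In a small study meant to give a first view of safety and efficacy, the reported P/F change would describe completers rather than everyone in whom suction was started.

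MAP has the same selection problem. It may have a second: if a breach is treated with fluid or norepinephrine and CNAP goes on, later MAP readings include that support.

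**Working it through.** **Inputs from the documents.** 20 patients; P/F stop at a fall above 20%; two-sided 0.05; one-way repeated-measures ANOVA. There is no sample-size calculation to reproduce, because 20 is a convenience sample.

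**Assumptions, not in the documents.** Four time points: Stage 1, Stage 2, Stage 3, and Stages 4 and 5 counted as one. Log P/F = patient level + fraction × patient response + reading error, with fractions 0, 1/3, 2/3, 1. A patient stops if P/F at Stage 2 or 3 is more than 20% below Stage 1, a log change below ln 0.8 = −0.223. The plan does not state the reference value for the fall.

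**Step 1: can a stop be ruled out?** The chance of at least one stop in 20 is 1 − (1 − p)^20. It is 18% for p = 1%, 64% for p = 5% and 88% for p = 10%.

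**Step 2: hand check of one case.** Take reading log SD 0.10 and patient log SD 0.25. At Stage 3 the change from Stage 1 has SD √[(2/3)² × 0.25² + 2 × 0.10²] = √0.0478 = 0.219, so P(stop) = Φ(−0.223/0.219) ≈ 0.15. At Stage 2 the SD is √[(1/3)² × 0.25² + 2 × 0.10²] = 0.164, and P ≈ 0.09. The chance of either lies between 0.15 and 0.24. The simulated 16.3 completers of 20 (18.5% stopped) fits.

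**Step 3: completers' P/F change at the last suction stage, true effect zero.**

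| Reading / patient log SD | Completers of 20 | Apparent change |
|---|---|---|
| 0.05 / 0.05 | 19.9 | 0.0% |
| 0.05 / 0.10 | 19.7 | +0.4% |
| 0.10 / 0.15 | 17.2 | +3.8% |
| 0.10 / 0.25 | 16.3 | +8.3% |
| 0.15 / 0.25 | 14.4 | +11.4% |

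With a true rise of 12%, completers show +12.0% (0.05/0.05), +14.3% (0.10/0.15) and +17.7% (0.10/0.25).

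**Step 4: rejection rate at 0.10/0.25, true zero on the log scale.**

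| Analysis | Completers | All 20 kept |
|---|---|---|
| Log P/F | about 28% | 8% |
| Log P/F, Greenhouse-Geisser | about 21% | 5% |
| Raw P/F, no correction | about 34% | 9% |

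The raw-scale row is not a clean null: a response SD of 0.25 alone raises the raw mean by exp(0.25²/2) − 1 = 3.2%. The log rows isolate selection better.

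**Step 5: a different stage model.** Assume baseline plus Stages 1 to 5, half the effect at Stage 2 and all of it from Stage 3, response SD 20%, reading SD 5%, and a true fall of about 10%. All 20 patients then average −7.4% and completers +2.3%.

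**Step 6: direction.** If the progression wording also holds responders (P/F up more than 20%) at an early stage, a true +12% appears as +10.8% (0.05/0.05), +5.8% (0.10/0.15) or +3.2% (0.10/0.25).

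**Step 7: MAP.** MAP stops at a rate of about 10%, unrelated to P/F, move the P/F mean by 0.0 to +0.3 points. On MAP itself, with a true fall of 5 mmHg and no breach corrected, completers show −4.9, −3.5 and −2.0 mmHg for assumed patient/reading SDs of 2/2, 6/4 and 9/4 mmHg. If breaches are treated, CNAP continues where that works, and support adds an assumed 5 to 10 mmHg, recorded MAP shows −4.5 to −3.9 mmHg (2/2) or −3.1 to −1.8 mmHg (6/4).

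**The case against.** The plan nowhere says that incomplete patients are dropped. A reader might infer that it does, but exclusion is only the usual behaviour of the named method. The missing flow chart and case report form may set the blood-gas schedule, the time points or what is recorded after a stop. This stands, and it makes the point conditional.

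A reader might also infer that every safety stop biases the P/F result. The text does not support that. MAP stops matter to P/F only if the two are related, and no SpO2 scenario was worked out. One P/F stop in 20, at −20% to −40% with completers at zero, moves the mean by only 20/20 = 1 to 40/20 = 2 points.

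Nor do the documents establish that a MAP fall will be masked. The stop rule's qualifier suggests that support may be tried first, yet the Protocol section calls for an immediate stop and SAFETY PROCEDURES says that no drugs will be given. Which applies is unclear.

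Finally, safety and efficacy are defined as per-patient thresholds, which can be counted over everyone started, and inspection of the data would show the stopped patients. That protects the event counts. It does not protect the ANOVA means and p-value, which are the only planned inference.

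**Conclusion.** The concern holds in conditional form. Three things must coincide: the ANOVA's time points are the stages, at least one patient is stopped early for P/F, and the usual complete-series form is used. The P/F comparison is then made in patients selected on P/F. At a true zero effect the shift runs from nil to about +11% over reading log SDs of 0.05 to 0.15 and patient log SDs of 0.05 to 0.25, all assumed. With little variation it is negligible.

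A reader might infer that the bias always favours CNAP. The documents do not settle this, because their progression wording could remove responders as well and reverse the sign. A reader might also take a false-positive rate of about a third as the cost of selection. That figure belongs to raw P/F without a sphericity correction; on the log scale with the correction, the comparison is about 21% against 5%.

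This should be fixed. Confidence is medium, because the SDs, the stop rate and the unseen flow chart decide the size.

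**What to change.** Replace the ANOVA paragraph with text along these lines:

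*Log P/F and MAP are each analysed with a likelihood-based mixed model with stage as a factor. The model uses Stage 1 and every value recorded under suction from all patients in whom suction was started, including the value at a stop. The within-patient covariance allows patients to differ in response. Standard errors use a small-sample method. One contrast with Stage 1, named before analysis, carries the p-value; the others are given with 95% confidence intervals. A stage reached by few patients is described without a test.*

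A random intercept alone is not enough. At true zero it still gives +1.4% (0.10/0.15) and +4.7% (0.10/0.25), whereas an unstructured covariance gives 0.0% to +0.7% across the five cases. The small-sample error matters too: ordinary standard errors with t on 19 df gave 5.6% to 10.1% false positives, against 3.8% to 5.7% for a leave-one-patient-out jackknife. The jackknife is one option, not a requirement.

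Report over all patients started: the number reaching each stage, each stop with its reason, the rate of P/F rises above 20% (stating in advance how stopped patients count), and MAP as recorded beside any fluid or norepinephrine given. An analysis of MAP before support is an optional sensitivity analysis.

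Two sets of passages must be reconciled by the sponsor: the progression wording at Stages 2 and 3 with the two-hour continuation after efficacy, so that it is clear which stages responders pass through; and the MAP qualifier with the immediate stop and the no-drugs statement.

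Cost: a rewritten paragraph, and support recorded by stage if the case report form does not already do so. No extra patients are needed. Downsides: a more complex model at n = 20 (an unstructured covariance has 4 × 5/2 = 10 parameters with four time points), a possibly smaller reported effect, and residual bias if stops depend on unrecorded values.
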